6.8 Early Termination Visit

Subjects who discontinue taking study drug early should, if possible, have an Early Termination visit as soon as possible after the subject stops taking study drug. Where possible the Early Termination visit assessments should be completed in the study center as listed below. Site staff will need to provide subjects with meals and snacks at appropriate times during the visit to ensure subjects have enough energy prior to completing the exercise tests.

- Review concomitant medications and non-drug treatments*
- Review of adverse events*

- Brief physical examination (including weight)
- Physician completion of subjects PMM phenotypic description
- 12-lead ECG
- Vital signs (including temperature) *
- Obtain blood samples for:
 - Hematology (incl HbA1c)*
 - Biochemistry*
 - Additional bone and calcium metabolism markers
 - Plasma sample for pharmacokinetic analysis of REN001 *
- Obtain second morning void urine sample for:
 - Bone marker – NTX*
 - Urinalysis*
 - Drugs of abuse*
 - Urine for pregnancy testing (WOCBP only) *
- MFIS*
- BPI*
- SF-36*
- PGIS – muscle symptoms*
- PGIS – fatigue symptoms*
- PROMIS Short Form – FACIT Fatigue 13a*
- PGIC muscle symptoms (with respect to how they were on their last dosing day) *
- PGIC fatigue symptoms (with respect to how they were on their last dosing day) *
- WPAI:SHP*
- 12MWT
- 30STS
- Capsule counts of remaining capsules including any opened IMP bottles*
- Eye examination (may be completed \pm 14 days of the visit if required)

If the subject is unable to attend the Study Center for the full visit, then every effort should be made to complete the assessments marked with an asterisk (*) at the discretion of the Investigator this may be completed over 2 days if feasible.

If the subject is withdrawing from the study: after their Early Termination Visit they should be instructed to return for the Follow Up Visit 21-28 days after their last dose of study medication. If the Early Termination Visit is 21 or more days after the last dose, then the Follow Up Visit is not needed.

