6.9 Subject Continuation In Study Off IMP

If a subject discontinues taking study drug, they will be strongly encouraged to continue in the study for their Week 12 and Week 24 visits (see [Figure 3](#)). If they agree to remain in the study off-IMP as a minimum they will be requested to complete the following assessments:

- Review concomitant medications and non-drug treatments
- Review of adverse events

- Vital signs (including temperature)
- MFIS
- 12MWT

Table 2: Schedule of Activities

Time and Events Table	Screening	Baseline ^{1, 2} (Day 1)	Week 2 ³ (Day 14)	Week 4 ³ (Day 28)	Week 8 (Day 56)	Week 12 ^{2, 4} (Day 84)	Week 16 (Day 112)	Week 18 ³ (Day 126)	Week 20 (Day 140)	Week 24 ^{2, 4} (Day 168).	Early Term ^{2, 5}	Follow Up ³ (21-28 days post last dose)
Visit number	1	2	3	4		5		6		7		8
Window (days)			±3	±3		±7		±7		±7		
Informed Consent	X											
Completion of Proforma and data entered into eCRF ⁶	X											
Demographics	X											
Medical/medication/drug/alcohol/tobacco history ⁷	X											
Physician completion of PMM phenotypic description		X								X	X	
Physical exam ⁸	X	X				X				X	X	
12-lead ECG	X	X				X				X	X	
Supine Vital signs (BP, PR and temperature)	X	X	X	X		X		X		X	X	X
Serum FSH ⁹	X											
HbA1c	X									X	X	
Hepatitis B/C/HIV	X											
Safety labs (inc. urinalysis)	X	X ¹⁰	X	X		X		X		X ¹¹	X	X ¹¹
Blood sample for bone and calcium markers		X				X				X	X	
Pregnancy Test (WOCBP only) ¹²	X	X		X	X	X	X		X	X	X	X
Blood sample for genotyping ¹³	X											
Population PK blood sample ¹⁴		X	X	X		X		X		X	X	
Urine drugs of abuse	X	X				X				X	X	
Urine NTX		X				X				X	X	

Time and Events Table	Screening	Baseline ^{1, 2} (Day 1)	Week 2 ³ (Day 14)	Week 4 ³ (Day 28)	Week 8 (Day 56)	Week 12 ^{2, 4} (Day 84)	Week 16 (Day 112)	Week 18 ³ (Day 126)	Week 20 (Day 140)	Week 24 ^{2, 4} (Day 168).	Early Term ^{n-2, 5}	Follow Up ³ (21-28 days post last dose)
Sites to provide appropriate snacks and lunch	X	X				X				X	X	
Pedometer eDiary data collection (inc. review)	X	X ¹⁵		X		X		X		X		
MFIS / PGIS (muscle symptoms), PGIS (fatigue symptoms) and PROMIS – Short form FACIT fatigue 13a	X	X		X		X		X		X	X	
SF-36 / BPI and WPAI:SHP		X		X		X		X		X	X	
PGIC (muscle symptoms) and PGIC (fatigue symptoms)										X	X	
12 Minute Walk Test	X ¹⁶	X				X				X	X	
30STS		X				X				X	X	
IMP Capsule Counts			X	X		X		X		X	X	
Eye examination	X ¹⁷					X				X	X	
Wrist radiograph	X ¹⁸											
Concomitant medication review	X-----X											

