Dosing		X ¹⁹ -----X										
AE collection and reporting	X-----X											

1. Screening visit must take place a maximum of 8 weeks before the Baseline visit.
2. If appropriate and feasible Baseline, Week 12, Week 24/Early Termination visits may be conducted over 2 days at the Investigators discretion.
3. In countries where the regulatory body allows, visit may be in the Study Center or a home nursing visit.
4. Only review of concomitant medications, AE's MFIS and 12MWT will be conducted if the subject has discontinued from study drug treatment but has not withdrawn from the study. If the subjects had an ET visit within 2 weeks of either of these a visit is not required.
5. As a minimum, subjects should have review of concomitant medication and AE's, vital signs (including temperature), complete questionnaires, safety laboratory blood (including HbA1c, bone and calcium markers and PK analysis) and urinalysis (including pregnancy tests for WOCBP, drugs of abuse and NTX) and IMP capsule counts.
6. Patient Screen Oversight Committee will review Proforma data and give a decision or request more information within 7 working days.
7. Subjects will be excluded from the study at the Investigators discretion for alcohol and/or drug dependency. Use of opiates/cannabis for medical reasons is acceptable with prescription evidence or at the Investigators discretion.
8. Full physical exam, height and weight at Screening; full physical exam and weight at Baseline; brief, symptom-directed physical exam and weight only at Weeks 12 and 24.

9. Serum FSH testing for postmenopausal females 45years and older.
10. An additional 10 mL blood sample will be taken pre-dose at baseline and the serum will be stored frozen at the central laboratory as a reference sample in the event that re-analysis of protocol stated tests are required.
11. If any clinically significant abnormalities are noted at the Week 24 visit, these should be followed up until resolved.
12. WOCBP will be supplied with urine home pregnancy test kits at Study Center visits to test at Weeks 8, 16 and 20. The Study Center must contact the subject to confirm the pregnancy test result in a timely manner.
13. Blood sample for local genotype testing will only be conducted with prior Sponsor approval and definitive results must be available prior to the Baseline visit.

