8.2. GENERAL METHODS

All statistical testing will be at the 5% level of significance (2-sided) and all point estimates for the comparison between treatment groups will be accompanied by 2-sided 95% confidence intervals. To preserve the Type 1 error a fixed sequence testing procedure will be adopted. Testing will be on the FAS. The order of testing for the primary and secondary endpoints will be:

1. Change from Baseline at Week 24 in distance walked during the 12MWT
2. Change from Baseline at Week 24 in the PROMIS T-score

Continuous variables will be summarized using the number of non-missing observations (n), mean, SD, median, minimum, and maximum. Categorical variables will be summarized using counts and percentages.

Unless otherwise specified, the estimated mean and median for a set of values should be displayed to 1 more decimal place than the original values, and SD should be displayed to 2 more decimal places than the original values. The minimum and maximum should be displayed to the same number of decimal places as the original values. Deviations from this convention may arise to take account of the relevance of the precision (e.g., the distance walked in the 12MWT is reported to the nearest cm, but there is no relevance in presenting the mean to the nearest mm). These deviations from convention will be documented in the relevant analysis sections below.

Percentages will be displayed with 1 decimal place; except percentages will not be presented when the count is zero and 100% will be presented as an integer. Unless stated otherwise, percentages of subjects will be based on the number of subjects with non-missing data in the analysis set used for the presentation.

Baseline will be taken as the last available non-missing assessment prior to study drug administration (Day 1). Although the time of completion is not collected for QoL questionnaires (MFIS, PGIS, PROMIS, SF-36, BPI or WPAI:SHP), any completed on Day 1 will be deemed suitable for baseline as the questionnaires are requested in the protocol to

be completed prior to dosing and, even if after dosing, there is no anticipated effect after a single dose.

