8.3.1. Efficacy Data

As missing data may potentially bias the outcome of the statistical analyses and the subsequent estimation of the magnitude of the treatment effect, different strategies will be applied to provide a balanced assessment of treatment efficacy. This section discusses intercurrent events and missing data in general, but details for each endpoint are discussed in [Section 10](#).

Intercurrent Events

The following potential intercurrent events are currently identified:

- Discontinuation of study treatment
- Specifically, for the 12MWT and 30STS; unwilling or unable to perform the test or walk for the full 12 minutes due to reasons at least possibly related to PMM or study treatment

Subjects who discontinue treatment will be encouraged, where appropriate, to continue in the study with a reduced assessment schedule at Weeks 12 and 24. As a minimum they will be requested to complete the 12MWT and MFIS efficacy assessments at these visits. This allows a treatment policy strategy to be used; for example, the distance walked at the relevant visit will be included in the analysis, regardless of whether the subject has previously discontinued study treatment.

If the subject is unable to perform the 12MWT and/or 30STS at a visit, for reasons at least possibly related to their PMM, their data will be imputed as 0 meters and/or 0 sit to stands for each test, respectively. To assess the subject as unable to perform the 12MWT there must be clear evidence that the subject is not ambulatory at the time of the test.

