8.4. VISIT WINDOWS

Data will be assigned to ‘analysis’ visits using windowing (see table below). If more than one assessment (including the early termination or unscheduled assessments) falls within the same defined window, the on-treatment assessment closest to the target day with non-missing data will be used for analysis. If the scheduled visit assessment is on-treatment and

within the analysis window, then this will be used irrespective of other unscheduled assessments within the analysis window. If two assessment dates are at the same distance from the target day, the latest on-treatment assessment with non-missing data will be used for analysis. Off-treatment assessments will only be assigned to a visit window in the absence of an on-treatment assessment within the analysis window.

Visit	Target Day	Protocol Visit Window	Analysis Window	Analysis Interval
Baseline	1	NA	$\leq 1^*$	NA
Week 2	14	± 3	8 - 20	13 (± 6)
Week 4	28	± 3	21 – 35 [^]	15 (± 7)
Week 12	84	± 7	63 -105	43 (± 21)
Week 18	126	± 7	106 - 146	41 (± 20)
Week 24	168	± 7	147 - 189	43 (± 21)

* Baseline values must be prior to dosing if time of assessment is recorded.

[^] For pedometer data the lower limit of the analysis window will be widened to allow for the fact that the diary opens 2 weeks prior to the target visit date (Day 14 – 35).

If an unscheduled or early termination visit is mapped to a scheduled visit, then the type of visit will be identified in the appropriate listing together with the visit that it has been mapped to.

Any summaries of screening visit data will always be based on the data collected at the scheduled screening visit. Consequently, if the subject does not have baseline data collected at the baseline visit then the screening data will be used for both the summary of the screening visit and the baseline visit.

Follow-up visits by design are after the last dose of study drug and should not be allocated to on-treatment visits.

Windowing will not be used for the DXA scan data as there is only one measurement post dose.

Data collected outside these windows will not be attributed to an analysis window and will only be listed; unless specified otherwise in [Section 10](#) and [Section 10](#). Any scheduled visit outside the window will be identified on the appropriate listing.

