14. CHANGES FROM PLANNED ANALYSES SPECIFIED IN THE PROTOCOL

- The secondary endpoints have been updated following FDA advice. The PROMIS T-score has been promoted to a secondary endpoint and MFIS physical sub-scale score and PGIC (muscle symptoms) have been moved to exploratory endpoints. The order of testing of endpoints has also been updated to align with this change.
- As the PGIC is assessed at the end of study treatment (Week 24 or Early Termination) a while on treatment strategy was proposed in the protocol. However, with some subjects not completing their PGIC assessment until more than a week after their last dose of study medication the strategy has been changed. The primary analysis will include all recorded data, regardless of the duration between the subject's last dose of study medication and the assessment. Given some subjects will have been off treatment for more than 7 days before recording PGIC, this analysis will no longer be referred to as a 'while on treatment' strategy; instead, this is a 'treatment policy' strategy. Subjects with no PGIC assessment will be considered as missing unless the incidence of missing PGIC data exceeds 5%. If the incidence exceeds 5% a multiple imputation approach will be used. A 'while on treatment' strategy has also been included as a supplementary analysis, where only assessments within 7 days of the last dose of study treatment will be included.
- A responder endpoint has been defined for the PGIC muscle symptoms and PGIC fatigue symptoms in addition to the 7-point scale endpoints.
- Two additional exploratory endpoints based on the 12MWD have been defined to further support the primary analysis. The endpoints are the first and last 6-minute periods of the 12MWD and aim to investigate whether there is a difference in treatment effect in these two periods.
- The supplementary analysis for the primary endpoint using a while on treatment strategy has been updated to an ANCOVA following review comments from the FDA. The original while on treatment analysis proposed in the protocol is now referred to as a treatment period restricted analysis.
- Added the exploratory endpoint for the phenotypic description questions (exercise tolerance, gait stability and myopathy) which are asked at Baseline and Week 24.

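### PROMIS is now the only secondary endpoint, but off-drug Week 12 and Week 24 visits still ask only for MFIS and the walk, so an obtainable Week 24 PROMIS score is imputed

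*Protocol*

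**What the plan says.** SAP 8.2 fixes the order of testing: the 12-minute walk first, then "Change from Baseline at Week 24 in the PROMIS T-score". SAP 14 records the switch, made on regulatory advice: "The PROMIS T-score has been promoted to a secondary endpoint and MFIS physical sub-scale score" and the PGIC for muscle symptoms moved down to exploratory.

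Subjects who stop study drug are encouraged to stay and attend Weeks 12 and 24 on a reduced schedule. Protocol 6.9 says that "as a minimum they will be requested to complete the following assessments", and its list holds MFIS and the 12MWT as efficacy measures. SAP 8.3.1 says the same: "As a minimum they will be requested to complete the 12MWT and MFIS efficacy assessments at these visits". Footnote 4 of the schedule, in Protocol Table 2 and again in SAP 3.4, opens with the word *Only* and ends: "MFIS and 12MWT will be conducted if the subject has discontinued from study drug treatment but has not withdrawn from the study".

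PROMIS is collected at the Early Termination visit, which should take place "as soon as possible after the subject stops taking study drug". If the full visit is not possible, "every effort should be made to complete the assessments marked with an asterisk". Those items include PROMIS but not the walk. SAP 8.4 then assigns scores to analysis windows: "Data collected outside these windows will not be attributed to an analysis window and will only be listed". The Week 24 window is Day 147 to 189.

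**The concern.** The off-drug list fitted the protocol, where MFIS Physical was the first secondary endpoint and had a treatment policy strategy. When PROMIS took over that role, the list stayed as it was. Off-drug visits now collect the demoted fatigue scale and not the promoted one.

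At stake is the only result after the primary that is under Type 1 error control. For subjects who stop drug and still come to Week 24, that result rests on an imputed score for a questionnaire they could have filled in that day. SAP 8.3.1 itself says that off-drug follow-up is what makes a treatment policy strategy possible. It secures this for the walk but not for PROMIS.

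Sites also receive two instructions. A minimum list lets them add PROMIS; the word *Only* does not.

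**Working it through.** **Plan's own figure.** None exists for PROMIS. The stated sample size of 186 is for the walk. A two-sample t-test with a 60 m difference, SD 125 m, two-sided 5% and 90% power gives 93 per arm (power 90.3%), so it reproduces. It says nothing about PROMIS.

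**The four off-drug lists side by side.**

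| Place | Efficacy measures named | Status of the list |
|---|---|---|
| Protocol 6.9 | MFIS, 12MWT | minimum |
| Protocol Table 2, footnote 4 | MFIS, 12MWT | only |
| SAP 3.4, footnote 4 | MFIS, 12MWT | only |
| SAP 8.3.1 | 12MWT, MFIS | minimum |

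PROMIS is in none of them. Protocol 6.9 also lists vital signs, which footnote 4 leaves out.

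**One subject followed through.** The subject stops drug early, stays in the study and attends Week 24.
- Walk: the SAP 8.3.1 table has a row for this case, and the recorded distance is used without imputation.
- PROMIS: not requested, so the Week 24 score is imputed.

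**When an Early Termination score fills the gap.** It counts as Week 24 if it falls on Day 147 to 189. Footnote 4 waives the Week 24 visit when the Early Termination visit is within two weeks of it: 168 − 14 = Day 154 to 168 + 14 = Day 182, all inside the window. The gap therefore concerns subjects whose Early Termination visit falls before Day 147 or does not take place.

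**What an earlier Early Termination score adds.** The PROMIS model uses Weeks 4, 12, 18 and 24. The first three windows cover Days 21–35 (15), 63–105 (43) and 106–146 (41): 15 + 43 + 41 = 99 of the 145 days from Day 2 to Day 146. That is an upper bound, because SAP 8.4 gives an on-treatment score at the scheduled visit precedence in the same window. If scheduled visits fall on target, Days 29–35 (7), 85–105 (21) and 127–146 (20) are displaced: 99 − 48 = 51 days. These are calendar days, not subjects. Such a score informs the imputation but does not replace the Week 24 value.

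**Leverage of one imputed score.** 200 randomized 1:1 is about 100 per arm.
- One 5-point step (the SAP's tipping-point increment): 5 / 100 = 0.05 T-points on the arm mean.
- Full permitted range: (83.6 − 30.3) / 100 = 0.53. This is a ceiling, not an estimate.

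**Modified full analysis set (mFAS).** SAP 7.5 requires an on-treatment 12MWD, and SAP 10.2.1 uses this set for the PROMIS on-treatment analyses. On-treatment means up to last dose plus 7 days.
- The Week 4 PROMIS is due on Day 28 ± 3, so Day 25–31.
- The earliest scheduled walk is Day 84 − 7 = 77, which needs a last dose on Day 77 − 7 = 70 or later.
- A subject with last dose on Day 31–69 can have an on-treatment PROMIS score. The subject stays in the set only through an Early Termination or unscheduled walk within 7 days of last dose.

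**The case against.** A reader might infer that the SAP leaves open which imputation rule applies to these scores. The text does not support that. SAP 8.3.1 lists stopping treatment as an intercurrent event for efficacy in general; only its second bullet is limited to the exercise tests. The schedule omits PROMIS because the subject stopped drug, so the natural reading is that the score is missing as a result of that event. SAP 8.3.1 then gives worst case if the event is related to PMM or study treatment, and missing at random if not. A blinded sponsor team adjudicates before lock. What remains is wording: the case-by-case table covers the 12MWT only, and SAP 10.2.1 mentions PMM where 8.3.1 has PMM or study treatment.

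A reader might also infer a large loss of power. An illustrative simulation, with every PROMIS input assumed (true difference 3.5, SD of change 6 to 10, 100 per arm), compared worst case with missing at random for all missing scores. With 10% against 5% missing, the estimate moved by about 1.1 to 1.3 T-points and power by 31 to 52 percentage points. With 5% in each arm, power moved by 4 to 7 points. This cannot be carried over to the trial. The plan splits scores by relatedness, and the illustration covers all missing scores, not only those of off-drug attenders.

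Three further points stand. The minimum wording allows PROMIS to be collected. The placebo-based pattern-mixture analysis covers missing data after discontinuation, though only as a sensitivity analysis. The standard Early Termination visit includes the walk, so loss from the mFAS needs a reduced visit, a late one or none.

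None of this puts PROMIS on the off-drug list.

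**Conclusion.** The point holds as a mismatch between the test sequence and data collection. Following the schedule as written, an off-drug subject who attends Week 24 and has no Early Termination PROMIS on Day 147–189 contributes an observed walk and an imputed PROMIS score. The conflict between *Only* and the minimum wording is plain in the text.

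The size of the effect cannot be derived. The documents give no discontinuation rate, no count of off-drug attenders and no SD of PROMIS change, and balanced counts would largely cancel. The only indirect figure, 1 − 186/200 = 7%, is an implied allowance for withdrawals from the study, not for subjects who stay off drug.

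The mFAS point is minor: it touches supplementary analyses outside the test sequence. The choice of imputation rule needs confirmation, not a new rule.

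**What to change.** 1. **Protocol amendment, then SAP.** Add PROMIS Fatigue 13a to the off-drug Week 12 and Week 24 assessments in Protocol 6.9 and Table 2 footnote 4. Reconcile *Only* with the minimum wording, and the vital signs entry with it. Then mirror the change in SAP 3.4 and 8.3.1; the SAP should not describe collection that the protocol has not requested. Cost: one 13-item questionnaire at visits already held, and a short amendment. It helps only subjects still to attend, who may be few given that SAP version 3.0 is dated 16 November 2023.
2. **SAP 7.5.** Define the mFAS per endpoint, so that PROMIS on-treatment analyses require an on-treatment T-score. Protocol 8.1.3 already ties the 12MWD condition to the primary endpoint. Cost: one line.
3. **Clarification before unblinding.** Align SAP 10.2.1 with 8.3.1, and confirm in one sentence that the related/unrelated rule covers PROMIS scores omitted by the off-drug schedule. Cost: two sentences.

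If collection is complete, items 2 and 3 still apply. Extending the tipping-point analysis to unrelated scores is optional.

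### The Early Termination waiver in Table 2 footnote 4 does not ask whether a 12MWT was done, so after a reduced ET visit the schedule no longer requires the Week 24 walk

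*Protocol*

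**What the plan says.** Footnote 4 of Protocol Table 2, repeated in SAP 3.4, covers the Week 12 and Week 24 visits of subjects who have stopped study drug. It gives a short list of assessments ending in the walk: "12MWT will be conducted if the subject has discontinued from study drug treatment but has not withdrawn from the study". It then adds the waiver: "If the subjects had an ET visit within 2 weeks of either of these a visit is not required". Nothing is said about what the ET visit contained.

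Protocol 6.8 lists the 12MWT in the full ET visit, to be done at the center where possible. It also provides for a shorter visit when someone cannot come in for all of it; for that case the instruction to sites is that "every effort should be made to complete the assessments marked with an asterisk". The 12MWT has no asterisk. Footnote 5 gives the ET minimum, which begins "As a minimum, subjects should have review of concomitant medication and AE's, vital signs (including temperature), complete questionnaires, safety laboratory blood" and goes on to urine tests and capsule counts. The walk is not in it.

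Protocol 6.9 says of subjects who stop drug that "they will be strongly encouraged to continue in the study for their Week 12 and Week 24 visits", and "If they agree to remain in the study off-IMP as a minimum they will be requested to complete the following assessments". That list contains the 12MWT. Section 6.9 does not mention the waiver.

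The primary endpoint is the Week 24 change in 12-minute walk distance under a treatment-policy strategy (Protocol 8.5.1, SAP 10.1.1). SAP 8.3.1 explains that requesting the 12MWT and MFIS from off-drug subjects is what allows that strategy.

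**The concern.** The waiver makes sense as a way to avoid two walks within two weeks. Its wording also covers an ET visit at which nobody walked. Suppose a subject stops drug on Day 156, has a reduced ET visit on Day 158 and agrees to stay in the study. Day 158 is 10 days before Day 168, so footnote 4 tells the site that Week 24 can be skipped, while Section 6.9 asks for that visit with a 12MWT. A site that follows the footnote exactly ends with no Week 24 walk for a subject it could still have invited.

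The treatment-policy estimand uses the distance observed after drug is stopped. Where the walk could have been done, an observed value is replaced by an imputed one, and only in subjects who discontinued. The imputation table in SAP 8.3.1 has no row for a walk missing because the schedule waived the visit. Adjudication must place it either in multiple imputation under MAR or in the worst-case draw.

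**Working it through.** **1. What the waiver leaves uncollected.** Compare the off-drug minimum in 6.9 with a reduced ET visit:

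| Item in the 6.9 minimum | Sought at a reduced ET visit (6.8 asterisk)? |
|---|---|
| Concomitant medications and non-drug treatments | Yes |
| Adverse events | Yes |
| Vital signs | Yes |
| MFIS | Yes |
| 12MWT | No |

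Only the primary measure is missing.

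**2. Whether an ET walk could stand for the visit.** The waiver range is the target day ± 14. SAP 8.4 gives the analysis windows.

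- Week 24: 168 ± 14 = Day 154 to 182, inside Day 147 to 189.
- Week 12: 84 ± 14 = Day 70 to 98, inside Day 63 to 105.

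An ET visit with a walk can therefore supply the visit value. An ET visit without one leaves the window empty unless a further walk is arranged, since the schedule has no other 12MWT between Week 12 and Week 24.

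**3. The plan's own sample size.** Difference 60 m, SD 125 m, two-sided 5%, power 90% (Protocol 8.2.2):

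n per arm = 2 × (1.960 + 1.282)² × 125² / 60² = 91.2, so 92. The t-based calculation gives 93, which is the stated 186 in total. The stated figure is reproduced. The margin up to 200 is (200 − 186)/200 = 7%; the documents state no discontinuation rate.

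**4. How many Week 24 walks are at risk.** Assumptions: discontinuations spread evenly over 168 days, and a prompt ET visit.

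- Upper figure: all 14 days before Day 168 count and every ET visit is reduced. Number = 200 × rate × 14/168.
- Lower figure: the Week 24 visit window is ± 7 days, so from Day 161 the site can hold the Week 24 visit itself. Only Days 154 to 160 count, and one third of ET visits are assumed to be reduced. Number = 200 × rate × 7/168 × 1/3.

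| Assumed rate | Stop drug | Lower | Upper |
|---|---|---|---|
| 7% | 14 | 0.2 | 1.2 |
| 10% | 20 | 0.3 | 1.7 |
| 20% | 40 | 0.6 | 3.3 |

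All of these still include subjects who leave the study altogether. The waiver does not apply to them, so the true figures are smaller.

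**5. Week 12.** At 10%, 20 × 28/168 = 3.3 ET visits fall within two weeks either side of Week 12, before the same reductions. A lost Week 12 walk costs information in the MMRM and the imputation model. It does not touch the primary timepoint.

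**6. Effect on the result.** Power by the normal approximation is 92.4% with 200 observed Week 24 values, 92.2% with 198 and 91.9% with 196. For the estimate, suppose one value in an arm of 100 becomes a worst-case draw of −200 to −400 m (assumed; the documents give no such figure). It contributes −2 to −4 m to that arm's mean, which is 2/60 = 3% to 4/60 = 7% of the design effect. The net shift is smaller by whatever loss the subject would really have shown. No comparable shift is shown for the MAR branch.

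**The case against.** The strongest reply is that footnote 4 only says a visit is not required. It neither cancels the visit nor forbids a walk, and 6.9 still strongly encourages it. A specific exception to a general request need not be a contradiction. The ordinary ET visit includes the walk, so the footnote reads naturally as avoiding duplication. The gap needs a reduced ET visit, a subject who stays in the study, and a date close to Week 24. A reduced visit happens only when the subject cannot attend the center for the full visit, and some of those subjects could not walk there two weeks later either. Figure 3, which sets out the discontinuation process, is not available here and may hold a further condition.

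Most of this stands, and it limits the size of the point. A reader might infer that the schedule removes the primary endpoint of subjects still in the study, at Week 12 as well as Week 24. The documents do not support that: the loss is permitted and not imposed, only Week 24 is the primary timepoint, and the subject stays in the FAS with an imputed value. A reader might also infer a bias between arms. Nothing in the documents shows that the loss would differ by arm, and the 2 to 4 m contribution applies only if adjudication chooses the worst-case branch.

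The reply does not supply the missing condition. Neither footnote 4 nor 6.9 says what to do when the ET visit had no walk, and 6.9 does not mention the waiver.

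**Conclusion.** The point holds as a gap in wording. After a reduced ET visit within two weeks of Week 24, footnote 4 ceases to require the walk that 6.9 requests as a minimum and that the treatment-policy estimand relies on. If the walk is then not done, the value goes to imputation, MAR or worst case as adjudicated.

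The size is small. With 10% of 200 subjects stopping drug evenly over 24 weeks, about 0.3 to 1.7 Week 24 walks are at risk, and fewer after removing study withdrawals. The discontinuation rate, its even spread, the prompt ET visit and the share of reduced visits are all assumptions. The effect on power is a fraction of a percentage point and the effect on the estimate is small. The sample size needs no change. Low severity: worth correcting because the correction is almost free, not because the result depends on it.

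**What to change.** Replace the waiver sentence in footnote 4 of Protocol Table 2 and of SAP 3.4 with wording such as: *If an ET visit that included a 12MWT took place within 2 weeks of the Week 12 or Week 24 visit, that visit is not required; otherwise the off-IMP visit with 12MWT (Section 6.9) should still be requested.* Add a reference to this condition in Section 6.9.

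The cost is a sentence in each footnote and a cross-reference in 6.9, by amendment or site memo. A very few off-drug subjects would be asked to attend a visit that 6.9 already requests.
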